## **6.6      Continued Access to Study Intervention after the End of the Study**

The Sponsor will **not** provide any additional care to participants after they leave the study because such care would not differ significantly from what is normally expected for patients with acute uncomplicated malaria due to *P. falciparum* infection. They will receive rescue treatment if the intervention fails to cure the disease and resolve the clinical event.

## **6.7      Treatment of Overdose**

For this study, any dose greater than the highest daily dose included in a clinical study protocol or planned for an individual participant enrolled in the study will be considered an overdose.

Even if not associated with an AE, SAE, or AESI, any overdose is recorded in the CRF and reported to global patient safety in an expedited manner. Overdoses are reported on a SAE and Overdose Report Form, following the procedure in [Appendix 4](#).

The effects of an M5717 overdose are unknown, and therefore no standard treatment is currently established. In the event of an overdose, the Investigator or treating physician should use appropriate clinical judgment for the evaluation and management of any clinical signs, symptoms, and laboratory results.

No case of overdosage with Pyramax has been reported. In cases of suspected overdosage symptomatic and supportive therapy should be given as appropriate, and transaminases (AST and ALT) should be monitored. If there are significant rises, then serial total and direct bilirubin values should also be obtained to determine whether there is any change in liver function.

Refer to package inserts of the rescue medication for details regarding the effects and management of an overdose.

## **6.8      Concomitant Therapy**

Record in the CRF all concomitant therapies (e.g., medicines or nondrug interventions) used from the time the participant signs the informed consent until completion of the study, including any changes. For prescription and over-the-counter medicines, vaccines, vitamins, and herbal supplements, record the name, reason for use, dates administered, and dosing information.

Contact the Medical Monitor for any questions on concomitant or prior therapy.

Participants will abstain from taking prescription or nonprescription drugs (including vitamins and dietary or herbal supplements) within 7 days (or 14 days if the drug is a potential enzyme inducer) or 5 half-lives (whichever is longer) before the start of study intervention until completion of the Follow-up Visit, unless, in the opinion of the Investigator and Sponsor, the medication will not interfere with the study.

Paracetamol, at doses of  $\leq$  2 g/24 hours, is permitted for use across the study. Ibuprofen, at doses of  $\leq$  1,600 mg/24 hours, is permitted for use across the study. Other concomitant medication may be considered on a case-by-case basis by the Investigator in consultation with the Medical Monitor if required. Paracetamol for fever is permitted when the temperature is  $\geq$  38.0°C.

### **6.8.1                   Rescue Medicine**

The following circumstances warrant discontinuation of study intervention or withdrawal from the study and the implementation of rescue medication:

1. Development of danger signs or signs of severe malaria in the presence of parasitemia on Days 1, 2, or 3, or a clinical requirement for parenteral treatment (WHO definition).
2. Parasitemia on Day 2 (48 hours) higher than Baseline count, irrespective of axillary temperature (WHO definition).
3. Parasitemia on Day 3 with axillary temperature  $\geq$  37.5°C (WHO definition).
4. Parasitemia on Day 3  $\geq$  25% of count at Baseline (WHO definition).
5. Parasitemia present on Day 8 (irrespective of the clinical state or temperature).
6. Vomiting the replacement dose within 2 hours of intake. (Note: If the participant vomits a dose within 1 hour of intake it may be replaced once. For each participant, a maximum of 2 doses may be replaced throughout the treatment schedule).

Rescue treatment involves therapy with an effective antimalarial available locally, preferably artemether-lumefantrine. Administration may be orally or parenterally depending on the participant's clinical condition.

The exact rescue regimen and route of administration must be recorded in the CRF on the concomitant medication page together with the start and end dates of the rescue medication applied. These participants will not be replaced.

### **6.8.2                   Permitted Medicines**

Any medicines that are considered necessary to protect the participant's welfare in emergencies may be given at the Investigator's discretion, regardless if it results in a protocol deviation.

### 6.8.3 Prohibited Medicines

The following products are considered as prohibited medication during the participant's participation in the study:

- Antimalarial compounds or products with antimalarial activity (macrolides, trimethoprim sulfamethoxazole, dapsone, rifampin, and cyclins) except for ophthalmic use (see [Appendix 7](#)).
- Medicines with mitochondrial toxicity, such as valproate and antiretroviral medicines should be avoided due to risk of overlap toxicity (see [Appendix 8](#); [Will 2019](#)).
- Medicines with photosensitivity risk such as tetracycline, doxycycline, nalidixic acid, voriconazole, amiodarone, hydrochlorothiazide, naproxen, piroxicam, chlorpromazine, and thioridazine (see [Appendix 9](#); [Drucker 2011](#)).
- Strong CYP3A4 inducers or strong CYP3A4 inhibitors ([FDA guidance for drug development and drug interactions 2020](#)).

Participants will not be withdrawn from the study due to the use of prohibited medication and the follow-up will be completed.

## 7 Discontinuation of Study Intervention and Participant Discontinuation/Withdrawal

### 7.1 Discontinuation of Study Intervention

If study intervention is permanently discontinued, the participant will remain in the study to be evaluated for end of follow-up. The Schedule of Assessments indicates data to be collected at the time of discontinuation of study intervention and follow-up, and for any further evaluations that need to be completed (see [Section 1.3](#)).

A participant will be discontinued from a study intervention (only applicable for Cohorts B2 and B3, in which 2- or 3-day treatment regimens are planned) if any of the following situations occur:

- LFT changes: study intervention will be discontinued on the second (Cohorts B2 and B3) and/or third day (Cohort B3) in a participant who develops jaundice or if a non-scheduled laboratory test shows an increase in transaminases and/or TB of  $\geq 3$ -folds compared to the Baseline value.
- CNS events: study intervention will be discontinued on the second (Cohorts B2 and B3) and/or third day (Cohort B3) in a participant who develops study intervention-related (according to Investigator's judgment) neurological TEAE.
- Pregnancy: pregnancy tests will be performed at Screening and Day 1, and the maximum study intervention will last 3 days in Cohort B3, making it extremely unlikely for a pregnancy to occur in this time period. Details are provided in [Section 8.3.4](#).
- ETF as specified in [Table 3](#) (Ref #3) warrants the discontinuation of study intervention and the administration of rescue medication (see [Section 6.8.1](#)).

## 7.2

## Participant Discontinuation/Withdrawal from the Study

- A participant may discontinue from the study at any time, at his/her own request or at the discretion of the Investigator for safety, behavioral, compliance, or administrative reasons.
- At the time of study discontinuation, if possible, a discontinuation visit will be conducted, as listed in the Schedule of Assessments. The Schedule of Assessments specifies the data to collect at study discontinuation and follow-up, and any additional evaluations that need to be completed.
- If withdrawal from the study occurs for any reason, the Investigator must determine the primary reason for a participant's withdrawal from the study and record this information on the Study Completion CRF.
- Protocol violations should not lead to participant withdrawal unless they indicate a significant risk to the participant's safety.
- If the participant revokes consent for the study, any data collected up to that point may still be used, but no future data can be generated, and any biological samples collected will be destroyed.
- A participant has the right at any time to request destruction of any biological samples taken. The Investigator will document this in the site study records and the CRF and inform the Sponsor. The samples will be destroyed.
- In case LFT derangements are observed, the IDMC would need to review the data; the participants who have been treated with M5717 will be followed up and might remain on the study, rather than being withdrawn, unless a decision is made otherwise by the Investigator or the IDMC.

If a participant has failed to attend scheduled study assessments, the Investigator must determine the reasons and the circumstances as completely and accurately as possible. If there is a medical reason for the withdrawal, the participant will remain under the supervision of the Investigator until satisfactory health has returned or care has been transferred to the participant's general practitioner or to a hospital consultant. In case a participant has to be withdrawn from the study, the Study Monitor and Clinical Study Leader will be informed immediately.

## 7.3

## Lost to Follow-up

A participant will be considered lost to follow-up if he or she repeatedly fails to return for scheduled visits and is unable to be contacted by the study site.

The following actions will be taken if a participant fails to return to the clinic for a required study visit:

- The site will attempt to contact the participant and reschedule the missed visit as soon as possible, counsel the participant on the importance of maintaining the assigned visit schedule and ascertain if the participant wants to or should continue in the study.

- Before a participant is deemed “lost to follow-up”, the Investigator or designee will make every effort to regain contact with the participant: 1) where possible, make 3 telephone calls; 2) if necessary, send a certified letter (or an equivalent local method) to the participant’s last known mailing address, and 3) if a participant has given the appropriate consent, contact the participant’s general practitioner or caretaker (where allowed by local regulations) for information. These contact attempts will be documented in the participant’s medical record.
- If the participant continues to be unreachable, he/she will be deemed as “lost to follow-up”.

## 8 Study Assessments and Procedures

- Study assessments and procedures and their timing are summarized in the Schedule of Assessments (see Section 1.3).
- **No** protocol waivers or exemptions are allowed.
- Immediate safety concerns are discussed with the Sponsor immediately upon occurrence or awareness to determine if the participant should continue or discontinue study intervention.
- Adherence to the study design requirements, including those specified in the Schedule of Assessments, is essential and required for study conduct.
- All Screening evaluations will be completed and reviewed to confirm that potential participants meet all eligibility criteria. The Investigator will maintain a Screening log to record details of all participants screened, to confirm eligibility, and if applicable, record reasons for screening failure.
- Prior to performing any study assessments that are not part of the participant’s routine medical care, the Investigator will obtain written informed consent as specified in Appendix 2.
- Procedures conducted as part of the participant’s routine medical care (e.g., blood count) and obtained before signing of the ICF may be used for Screening or Baseline purposes provided the procedures met the protocol-specified criteria and were performed within the time frame defined in the Schedule of Assessments.
  - No more than 3 mL/kg of blood may be drawn in a 24-hour period, and no more than 9 mL/kg of blood in a 4-week period. Maximum blood volumes to be withdrawn are detailed in Section 2.3.1, according to the bodyweight and hematocrit value.
  - Where allowed by local law/regulations, samples collected during this clinical study may be transferred to a biobank and used for future research outside the clinical protocol when additional consent for this purpose is given. Transfer to the biobank will be documented and any testing of coded biobank samples will **not** be reported in the CSR.
  - The long-term storage of samples after study completion for future research may be performed will all sample types collected in the study (e.g., PK, CCI [REDACTED] if the participant consents to optional future medical research.

## 8.1 Efficacy Assessments and Procedures

### Assessment of Primary Efficacy Endpoint

The primary efficacy endpoint of Part B of the study is defined by PCR-adjusted ACPR 28 days after first treatment (note that the primary endpoint of Part A is related to safety). ACPR is defined as absence of parasitemia (thick smear/microscopy, after adjustment for parasitemia due to new infections as determined by genotyping using PCR techniques), irrespective of axillary temperature, in participants who did not previously meet any of the criteria of ETF, LCF or LPF. ETF, LCF and LPF are defined according to WHO guidelines (WHO 2021, see also [Table 3](#)). PCR-adjusted ACPR is defined as clearance of asexual parasitemia within 7 days of initiation of study treatment and without recrudescence within 28 days of initiation of study treatment. New infection (with a different parasite stem as compared to primary infection) as evidenced by PCR genotyping studies will not be considered a treatment failure.

### Assessment of Secondary Efficacy Endpoints

For the definitions of secondary efficacy endpoints please refer to [Table 3](#).

Recrudescence is defined as reappearance of parasites of the same isolate as initial infection, with or without clinical signs, after initial clearance of parasites from the peripheral blood, with positive blood smear and PCR genotyping confirmation of the same isolate.

The time to fever clearance is defined as the time from first dosing to the first normal reading of temperature ( $< 37.5^{\circ}\text{C}$ ) for 2 consecutive normal temperature readings plus confirmed normal temperature 24 hours after the first normal body temperature reading. The method of temperature measurement must be the same (axillary) for all measures in the same patient. Those participants who are initially included on documented history of fever and who do not subsequently have a documented temperature reading of  $> 37.5^{\circ}\text{C}$  during the 24 hours following initial dosing, will not be included in this endpoint analysis.

The parasite clearance time represents the time from first dosing to time of first blood draw with parasite clearance. Parasite clearance is defined as zero presence of parasites for 2 consecutive negative readings at least 6 hours apart.

The PRR index is defined as  $\frac{C_{48}}{C_0} - 1$ , where  $C_{48}$  is the parasite count at 48 hour and  $C_0$  is the count at pre-dose on Day 1 (Baseline).

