To describe the clinical efficacy of the M5717-pyronaridine combination in adult participants with acute uncomplicated malaria due to P. falciparum	
Endpoint: ETF defined as meeting any of the following:
 
 
Danger signs or severe malaria 1, 2, or 3 days after treatment, in the presence of parasitemia
 
Parasitemia 2 days after treatment higher than on day of treatment, irrespective of axillary temperature
 
Parasitemia 3 days after treatment with axillary temperature <math>\geq 37.5^{\circ}\text{C}</math>
 
Parasitemia 3 days after treatment <math>\geq 25\%</math> of count on day of treatment
 
 
Target Population: Adult patients with acute uncomplicated malaria due to P. falciparum
 
Treatment: Single dose M5717 330 mg plus pyronaridine 360 mg
 
Intercurrent Event Strategy:
 
 
Intake of rescue medication before or at Day 4: Composite variable strategy, i.e., endpoint is considered as failure (= presence of ETF)
 
Intake of prohibited medication that impacts treatment effect (e.g., drug with antimalarial activity) before or at Day 4: Principal Stratum strategy, i.e., treatment effect is estimated within the principal stratum of participants that potentially don't experience the ICE
 
Experience of any event that affects absorption (i.e., vomiting within the study intervention absorptive period of <math>2 \times</math> median <math>t_{max}</math>) or immune response (severe immunocompromised participants): Treatment policy strategy, i.e., treatment effect is estimated regardless of intercurrent event or Principal Stratum strategy
 
Premature study discontinuation before or at Day 4 due to lack of efficacy: Composite variable strategy
 
Death due to malaria before or at Day 4: Composite variable strategy
 
 
Population-level Summary: ETF rate, i.e. proportion of participants with ETF.
	3

Objectives	Estimands/Endpoints	Ref. #

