	
Endpoint: Crude (PCR-uncorrected) efficacy 8 days after treatment, defined as absence of parasitemia (thick smear/microscopy) in participants who did not previously meet any of the criteria of ETF or LCF
 
Target Population: See endpoint 3
 
Treatment: See endpoint 3
 
Intercurrent Event Strategy: See endpoint 3
 
Population-level Summary: Crude efficacy rate, i.e., proportion of participants with crude (PCR-uncorrected) efficacy 8 days after treatment (Day 9)
	8
	
Endpoint: PCR-adjusted efficacy 8 days after treatment as defined as absence of parasitemia (thick smear/microscopy, after adjustment for parasitemia due to new infections as determined by genotyping using PCR techniques) in participants who did not previously meet any of the criteria of ETF or LCF
 
Target Population: See endpoint 3
 
Treatment: See endpoint 3
 
Intercurrent Event Strategy: see endpoint 3
 
Population-level Summary: PCR-adjusted efficacy rate, i.e., proportion of participants with PCR-adjusted efficacy 8 days after treatment (Day 9)
	9
	
Endpoint: PRR defined as decrease in viable parasites over 48 hours, corresponding to 1 asexual parasite life cycle
 
Target Population: See endpoint 3
 
Treatment: See endpoint 3
 
Intercurrent Event Strategy: see endpoint 3
 
Population-level Summary: Geometric mean of the PRR
	10

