#### 5.1 Inclusion Criteria

Participants are eligible to be included in the study only if all the following criteria apply:

Category	Criterion
Age:	1. Are $\geq 12$ and $\leq 55$ years of age ( $\geq 18$ and $\leq 55$ years of age for Part A) at the time of signing the informed consent.
Type of Participant and Disease Characteristics:	2. Microscopic confirmation of acute uncomplicated P. falciparum using Giemsa-stained thick and thin film. 3. P. falciparum parasitemia of $\geq 1,000$ to $\leq 50,000$ asexual parasites/ $\mu$ L of blood in Part A and P. falciparum parasitemia of $> 1,000$ to $\leq 150,000$ asexual parasites/ $\mu$ L of blood in Part B. 4. Axillary temperature $\geq 37.5^{\circ}\text{C}$ or tympanic temperature $\geq 38.0^{\circ}\text{C}$ (use as per COVID-19 protocols at the site [only at Screening]), or history of fever during the previous 24 hours (at least documented verbally).
Weight:	5. Have a body weight $\geq 24$ kg.

Category	Criterion

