Fever clearance time defined as the time from first dosing to the first measurement of an axillary temperature $< 37.5^{\circ}\text{C}$ for 2 consecutive temperature readings plus confirmed normal temperature 24 hours after the first normal body temperature reading	Median fever clearance time will be estimated by use of the Kaplan-Meier method separately for the one dose, the 2-day regimen, and the Pyramax treatment groups. A log-rank test will be applied to descriptively investigate differences between both treatment arms. In order to explore whether there is an impact of other covariates and factors, like, e.g., age, body weight, and baseline parasitemia on time to fever clearance a Cox Proportional Hazards model will be applied.	11, 28
PCT defined as time from dosing to the first negative (no parasites) film (microscopy)	Same as fever clearance time	12, 29
PRR defined as decrease in viable parasites over 48 hours, corresponding to one asexual parasite life cycle.	Geometric means of PRR will be estimated separately for participants of the single dose, the 2-day regimen and the Pyramax treatment arm together with 95% CIs. In order to investigate the impact of possible factors and covariates on PRR, a linear regression model will be used.	10, 27
Time to recrudescence, defined as the time from primary cure to the re-emergence of the same parasite strain that originated the primary infection.	Same as fever clearance time	13, 30

	Statistical Analysis	Ref. #
Time to re-infection, defined as the time from primary cure to the re-emergence of a different parasite strain that originated the primary infection.	Same as fever clearance time	14, 31
Time to re-emergence, defined as the time from primary cure to having recrudescence or re-infection (the first one that occurs).	Same as fever clearance time	15, 32

CCI

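### As printed, the parasite reduction index C48/C0 − 1 is zero or negative unless counts rise, so its prescribed geometric mean cannot be calculated

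*Protocol*

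**What the plan says.** Three parts of the protocol have to work together.

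- **Formula.** Section 8.1, under the secondary efficacy endpoints: "The PRR index is defined as" C48/C0 − 1, with C48 the parasite count at 48 hours and C0 the Day 1 count before dosing.
- **Meaning and summary.** Table 3, endpoint 10 (Part A): "PRR defined as decrease in viable parasites over 48 hours", with the population-level summary "Geometric mean of the PRR". Endpoint 27 in Table 4 (Part B) takes its summary from endpoint 10.
- **Analysis.** Table 9: "Geometric means of PRR will be estimated separately for participants of the single dose, the 2-day regimen and the Pyramax treatment arm", each with a 95% confidence interval, plus a linear regression for covariates.

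The protocol gives no sign change, offset or log transformation for this index, and no rule for a count of zero at 48 hours.

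**The concern.** A geometric mean is the exponential of the average logarithm, so every value must be above zero. The printed index is a signed relative change, and it is negative for exactly the participants in whom treatment is reducing parasites. The formula and the summary cannot both be applied. The sign also runs against the endpoint's own description, since a fall in parasites gives a negative number.

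At stake is a named secondary endpoint in both parts of the study. If it is reported, someone must choose a workable definition, and a treatment of zero counts, after the data are available. The possible choices do not give the same answer.

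**Working it through.** The plan states no figure for PRR, so there is nothing to reproduce. The check is whether the formula can feed the summary.

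**Inputs.** C48 is a count, so C48 ≥ 0. Inclusion criterion 3 (Section 5.1) sets parasitemia per microlitre from 1,000 to 50,000 in Part A, and above 1,000 up to 150,000 in Part B. That film is taken at screening and C0 is the pre-dose film, so I assume C0 is also above zero. Planned sizes are 12 in Part A and 25 in Cohort B0.

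**Range of the index.** Since C48/C0 ≥ 0, the index is never below −1. It is ≤ 0 exactly when C48 ≤ C0, and positive only when C48 > C0.

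| C0 | C48 | C48/C0 − 1 | C0/C48 |
|---|---|---|---|
| 50,000 | 0 | −1.00 | infinite |
| 50,000 | 500 | −0.99 | 100 |
| 50,000 | 12,500 | −0.75 | 4 |
| 50,000 | 50,000 | 0 | 1 |
| 50,000 | 60,000 | +0.20 | 0.83 |
| 150,000 | 150 | −0.999 | 1,000 |

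**Who gives a positive value.** Only participants with C48 > C0. That is the comparison in the early treatment failure criterion "Parasitemia 2 days after treatment higher than on day of treatment, irrespective of axillary temperature" (Table 3, endpoint 3). Taken literally, the geometric mean exists only among participants who meet that criterion.

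**Trying the summary.** I used illustrative data, assuming falls of 1 to 4 log10 by 48 hours.

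- Every index value lies between about −1.00 and −0.91.
- exp(mean of log) is undefined for n = 12 and for n = 25.
- The nth root of the product has absolute value 0.988 (n = 12) and 0.983 (n = 25). The product is positive for 12 and negative for 25, so the sign shows only whether n is even or odd.

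**Would an arithmetic mean rescue it?** It can be computed but hardly discriminates. A 10-fold fall gives 1/10 − 1 = −0.90, a 100-fold fall −0.99 and a 1,000-fold fall −0.999.

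**Ratio scale, same illustrative data.** The geometric mean of C0/C48 is 453 (n = 12) and 211 (n = 25) when all 48-hour counts are positive. With three zero counts, the geometric mean of C0/C48 is infinite and that of C48/C0 is 0. Changing the formula is therefore not sufficient; a rule for zeros is needed as well.

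**How much a zero rule matters.** Suppose k of n zeros are replaced by a limit L. Dividing L by a factor f multiplies the geometric mean of C0/C48 by f^(k/n). With three zeros, halving L multiplies it by 2^(3/12) = 1.19 in Part A and by 2^(3/25) = 1.09 in Cohort B0. The effect grows with the share of zeros.

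**The case against.** **The formula may be a misprint of an exponent.** If (C48/C0) to the power −1 was meant, the index is C0/C48. That is positive, agrees with the word for a fall, and suits a geometric mean. This cannot be excluded. The supplied text shows a subtraction without brackets, so it should be checked against the typeset page. Even if it is right, a participant with no parasites seen at 48 hours contributes C0/0. Films are read every 6 hours to 72 hours and clearance is itself an endpoint, so zeros are foreseeable, and no rule covers them.

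**A statistician could work around it.** −0.99 is a valid 99% relative fall. One could take the geometric mean of C48/C0, which is the index plus 1, and subtract 1 afterwards. Protocol Section 9.4 also leaves uncovered details to the analysis plan. This shows that the repair is easy and that the failure belongs to the literal instruction. It is still not what the protocol says, and one zero count forces the result to −1.

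**It is a minor endpoint.** True: PRR has no hypothesis test, power statement or decision rule. Cohorts B1 to B3 were not enrolled (SAP Section 7), so the comparison across arms falls away and only Part A and Cohort B0 remain.

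**Two stronger readings are tempting and not supported.** A reader might infer that the SAP dropped PRR without saying so, because its readable endpoint tables skip endpoints 10 and 27. But Section 7 has a blacked-out bullet between those for endpoints 8, 9, 25, 26 and 13–15, 30–32, and further redactions follow Section 14.6. PRR may have been dropped, moved or redefined there, so the SAP shows neither a repair nor a repetition of the fault. A reader might also say that the protocol describes a fold reduction which the formula fails to deliver. The protocol speaks only of a decrease; the ratio scale is a remedy, not something it already promised.

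**Conclusion.** The concern holds for the protocol as printed. The index is zero or negative for every participant whose count does not rise by 48 hours, so the prescribed geometric mean and its interval cannot be calculated for them. The only values that qualify come from participants meeting the 48-hour failure criterion. This follows from the algebra for any C0 above zero and does not depend on the illustrative data.

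It rests on reading the formula as a subtraction. Under the superscript reading the sign problem disappears, but the missing rule for zero counts remains, so the definition needs repair either way. The consequence is confined to one descriptive secondary endpoint in each part; the primary endpoint and the sample size are untouched. No conclusion is drawn about the SAP.

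**What to change.** 1. In Protocol Section 8.1, define PRR as C0/C48, or equivalently log10(C0) − log10(C48). Keep the geometric mean, with its 95% interval computed on the log scale and back-transformed. A fall is then above 1 and a rise below 1.
2. Pre-specify one rule for C48 = 0. Either:
   - substitute the microscopy detection limit and report how many counts were zero; or
   - treat those values as right-censored at that limit and use a censored-data estimate or the median. If more than half are zero, the median can be stated only as a lower bound.

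   The two should not be mixed: a plain geometric mean after substitution ignores the censoring.
3. State the numerical limit. The protocol does not give it and leaves the counting method to the Laboratory Manual, so it should be taken from there.

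The cost is one formula, one zero-count rule and one stated limit. The pre-dose and 48-hour films are already scheduled in Table 2, so no new data are needed. The small downside is that the result depends somewhat on the chosen limit, and more so as zeros become common.
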